All hypothesis tests comparing active and sham treatment will be two-sided and conducted at the 5% significance level based on Part A of the study. The primary population for assessing efficacy and safety will be the ITT population from Part A. A secondary analysis of the individual efficacy endpoints will be conducted using the Per-Protocol population from Part A. All summary tables will be presented by treatment group and over all patients in the analysis population being summarized. Continuous variables will be summarized using the following descriptive statistics: n, mean, SD, median, minimum, and maximum. Categorical variables will be summarized using counts and percentages. Percentages presented will be calculated using all patients in the analysis population being summarized (with randomized or received treatment as/if appropriate) as the denominator.

To compare the absolute change in pain from baseline to 4months, the intra-patient change will be calculated and serve as the dependent variable in the analysis. The baseline pain score will be introduced in the model as a covariate. Clinical site will be added to the model to assess poolability of the data across sites. Interaction between clinical site and treatment will be evaluated using a type 1 error rate of 10%.

Treatment-emergent adverse events will be summarized by study part, type, frequency, severity, and relationship to the study device. Adverse events will be provided in a listing.

SAS® Version 9.4 or later will be used to produce all statistical tables, listings and figures to be contained in the integrated statistical/clinical report.

Table of Contents

1.	INTRODUCTION AND BACKGROUND	.19
2.	STUDY OBJECTIVES	.24
3.	STUDY DESIGN	.25
3.1	Study Design	. 25
3.2.	EFFICACY ENDPOINTS	.26
3.3	SAFETY EVALUATION	.26
3.4	Eligibility Criteria	. 27
3.5	ENROLLMENT	. 30
3.6	RANDOMIZATION	. 30
3.7	DEVICE DESCRIPTION	. 30
3.7.1	Control Unit	. 30
3.7.2	Treatment Applicator	. 32
3.8	LOGISTICS AND DEVICE ACCOUNTABILITY	. 32
3.9	LABELING	. 33
3.10	Preparation and Administration	. 33
3.11	Blinding	. 33
3.12	Study Assessments	. 34
3.12.1	Primary Efficacy Assessment	. 34
3.12.2	Secondary Efficacy Assessments	. 34
3.12.3	Exploratory Efficacy Assessment	.37
3.12.4	Additional Study Assessments	. 38
3.12.5	Safety Assessments	. 40
4.	STUDY PROCEDURES	.40
4.1	VISIT 1 – SCREENING VISIT (DAY -15)	.40
4.2	14-Day Run-In Period	.42
4.3	Visit 2 – Enrollment Visit (Day 0)	.42
4.4	Day 7 Phone Call (Day 7 +2 Days)	.43

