3.1.1. Efficacy Assessments and Endpoints

There will be 11 total endpoints from Part A of the protocol (Part B analysis is in a separate SAP); the interest will be in the change from baseline and the differences between active Provant therapy vs. sham.

Primary Endpoint: Absolute change from baseline in pain intensity as measured by the 11-point, numerical pain rating scale (NPRS) (0-10; where 0=no pain, to 10=worst possible pain) through 4 months.

Secondary Endpoint 1: Percentage of patients who have either a 2 point or 30% reduction in NPRS at 4 Months.

Secondary Endpoint 2: Time to 30% or 2-point reduction in NPRS, whichever comes first at 4 Months.

Secondary Endpoint 3: Change in neuropathy related quality of life (NeuroQoL) between baseline and end of treatment at 4 Months.

Secondary Endpoint 4: Changes in Skin Perfusion Pressure (SPP) from baseline to end of treatment at 4 Months.

Secondary Endpoint 5: Changes in Nerve Conduction Studies (NCS) of Velocity and/or Amplitude between baseline and end of treatment at 4 Months.

Secondary Endpoint 6: Changes in Quantitative Sensory Testing (QST) between baseline and end of treatment at 4 Months.

Secondary Endpoint 7: Change in Patient Global Impression (PGI) at 4 Months.

Exploratory Endpoint 1: Change in Work Productivity and Impairment Questionnaire (WPAIQ) **Exploratory Endpoint 2:** Changes in intraepidermal nerve fiber density (IENFD) at the distal thigh.

Exploratory Endpoint 3: Changes in IENFD at the distal leg.

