4.3. Sample Size Justification

This is a Phase III study with a sample size of 170 patients (85 per treatment group). The sample size for the trial has been set at 170. Based on a previously conducted clinical trial assessing the efficacy and safety of the Provant Therapy System in a similar population, the mean \pm standard

November 7, 2018

deviation change in the NPRS from baseline to 60 days was 1.79 ± 1.83 units. The data are derived from the open-label, single arm part of the trial in which all subjects received PEMF. Assuming a placebo effect of 40% results in an assumed between group difference of 1.07 units. Based on alpha = 0.05 and 90% power, a sample size of 62 patients per treatment group would be needed based on a two-sided sample t-test for the NPRS. A total sample size of 162 was estimated based on enrolling 1.3 times the target sample size of 124 patients (124 * 1.3 = ~162).

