The Level 3 displays will report the paired results for the change from the baseline through Month 4. For example, if 18 subjects complete the baseline evaluation and 16 subjects complete the Month 4 visit, the difference (Month 4 minus Baseline) will contain 16 subjects.

Supportive individual subject data listings will be sorted and presented by subject number and visit date, if applicable. Listings will also include the number of days relative to the initial study treatment (active or sham).

Specific algorithms are discussed for imputing missing or partially missing dates, if deemed appropriate, under specific data topics. Imputed or derived data will be flagged in the individual subject data listings. Imputed data will not be incorporated into any raw or primary datasets. The imputed data will be retained in the derived / analysis datasets.

The total duration for a subject *on-study* will be calculated as the difference between the date of initial study treatment (active or sham) and the last day of observation plus 1 day. All calculations for defining the duration on-study will follow the algorithm DURATION = [STUDY COMPLETION OR WITHDRAW DATE – INITIAL TREATMENT DATE + 1].

This section details general conventions to be used for the statistical analyses. The following conventions will be applied to all data presentations and analyses.

- Summary statistics will consist of the count and percentage in each level for categorical variables, and the sample size (n) mean, median, standard deviation (SD), minimum, and maximum values for continuous variables.
- All mean and median values will be formatted to one more decimal place than the measured value. Standard deviation values will be formatted to two more decimal places

than the measured value. Minimum and maximum values will be presented with the same number of decimal places as the measured value.

- The number and percentage of responses will be presented in the form XX (XX.X%).
- All probability values will be rounded to four decimal places. All p-values that round to 0.0000 will be presented as '<0.0001' and p-values that round to 1.0000 will be presented as '>0.9999'. P-values <0.05 will be considered to be statistically significant.
- All summary tables will include the analysis population sample size (i.e., number of subjects).

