7.1. Adjustments for Covariates

The analyses will be adjusted using the baseline results that are found to differ between the randomized treatment groups to increase the precision of the model; the underlying assumption for inclusion of a covariate or covariates will be examined. Unadjusted analyses will also be conducted and reported as the first set of analyses presented.

Small sites (i.e., sites that have less than 2 patients for any of the treatment arms) will be identified and the following method will be used for combining the data. Data from all small sites will be combined to form a single site in order to obviate non-estimable situations (i.e., at least 2 observations are needed to estimate variance) in the evaluation of the performance of the

Version 3.0 Confidential Page 14 of 31

November 7, 2018

device by site. Once combined, the pooled site will remain as such for all analyses for which a site interaction effect is determined. If the pooled smaller sites represent a single site that has more than twice as many patients as the largest single site, however less than 3 times as many patients, the small sites will be ranked by size and divided into 2 pooled assignments using an alternating sequence (ABABAB). If the pooled smaller sites represent a site that has more than three times as many patients as the largest single site, however less than 4 times as many patients, the small sites will be ranked by size and divided into 3 pooled assignments using an alternating sequence (ABCABCABC). This methodology will be applied, based on the initial pooling of the smaller sites.

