11. EFFICACY EVALUATIONS

The primary endpoint for the study is the change from baseline in the NPRS score at 4 months. The primary hypothesis to be tested is presented below:

Ho: μ (Change in NPRS score at 4 months / PEMF group) = μ (Change in NPRS score at 4 months / sham group)

Ha: μ (Change in NPRS score at 4 months / PEMF group) $\neq \mu$ (Change in NPRS score at 4 months / sham group)

To compare the absolute change in pain from baseline to 4-months, the intra-patient change will be calculated and serve as the dependent variable in the analysis. The baseline pain score will be introduced in the model as a covariate. Clinical site will be added to the model to assess poolability of the data across sites. Interaction between clinical site and treatment will be evaluated using a type 1 error rate of 10%. A Mixed Models with Repeated Measures (MMRM) analysis comparing results across all time-points will also be performed, adjusted for the baseline value, week, treatment by week interaction and the effect of the patient.

The primary efficacy endpoint will be summarized and reported using the Level 3 table design. Results will be presented in Table 14.4.1.1 entitled Summary of the Pain Intensity by Randomized Treatment Assignment and Time (ITT Population)

Listing 16.2.8.1 entitled *Pain Intensity by Randomized Treatment Assignment and Time* will contain all of the recorded information; this listing will be sorted by subject number and relative study day.

A list of additional summary tables is presented in the table below.

Table	Description
14.4.1.1.1	Kaplan-Meier Estimates for the First Week where a Mean Reduction of 2 Points or a 30% Reduction from Baseline in the NPRS is Observed
14.4.1.1.2	Summary of the Pain Intensity Categorized by Success (>=30% reduction from baseline) by Randomized Treatment Assignment and Time
14.4.1.1.3	Summary of the Pain Intensity Categorized by Success (>=2 point reduction from baseline) by Randomized Treatment Assignment and Time
14.4.1.1.4	Summary of the Pain Intensity Categorized by Success (>=2 point reduction or 30% reduction from baseline) by Randomized Treatment Assignment and Time

Table	Description
14.4.1.2	Summary of the NeuroQoL Results by Question, Randomized Treatment Assignment and Time
14.4.1.2.1	Summary of the Efficacy Endpoints by Randomized Treatment Assignment and Time - NeuroQol (Weighted) Domain 1: Pain

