13.2. SAS Code for Generic Statistical Procedures

Note: Not all procedures may be required for the presentation of the results from this study. Information provided for procedures not directly referenced in this SAP may be used in supportive analyses.

1) SAS code for Kaplan-Meier analyses

```
PROC LIFETEST PLOT=(S) DATA = thedataset;
TIME DAY*CENS(1);
STRATA group;
```

CENS: Censoring variable: CENS=1 if censored, 0 otherwise.

DAYS: Time to event or censoring. group: group to test for differences.

Note: Survival probabilities are determined from the SURVIVAL variable in the PRODUCTLIMITESTIMATES ODS data set. Survival probabilities are determined at the observed values of the time variable. Survival probabilities at other days can be determined as the last survival probability up to the specified day.

2) SAS code for Cox analyses

Dummy variables must be constructed for center and treatment. If there are C centers, construct C-1 dummy variables as

```
CENTER_2 = (CENTER = second center number); ...

CENTER_C = (CENTER=last center number);
```

Note that one arbitrarily chosen center is not accorded a dummy variable.

For treatment, construct a dummy variable XXX treatment groups:

```
XXX = (TREAT = "XXX");
```

The control group is not accorded a dummy variable. Note: the coding of interactions must be determined.

The SAS code for the full model is then (replacing ... with full list of variables):

```
PROC PHREG DATA=input-data-set;
MODEL DAY*CENS(1) = TREATMENT CENTER_2 ... CENTER_C BASELINE;
OVERALL CENTER: TEST CENTER 2,..., CENTER C;
```

CENS: Censoring variable: CENS=1 if censored, 0 otherwise. The observation will be censored if the patient finishes the study or discontinues without responding.

Regenesis Biomedical, Inc. Protocol RBI.2017.002 Statistical Analysis Plan

Analysis Plan November 7, 2018

DAY: Time to event or censoring. CSTRATUM: Study center (stratum).

TREAT: Treatment.

Note: Survival probabilities are determined from the SURVIVAL variable in the output file. Survival probabilities are determined at the observed values of the DAY variable. Survival probabilities at unobserved days can be determined as the last survival probability at the observed day before the desired day. In this study it is likely (but not certain) that the median times will occur on an observed day.

Calculation of confidence intervals for the hazard ratio

The 95% confidence interval on the hazard ratio is calculated with the following formula:

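### Secondary Endpoints 3 to 6 (NeuroQoL, SPP, NCS, QST) have no firmly prespecified model with their own baseline: adjustment is imbalance-triggered, optional, or left to non-binding generic code

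*SAP*

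**What the plan says.** SAP 3.1.1 lists the Part A endpoints and says that "the interest will be in the change from baseline and the differences between active Provant therapy vs. sham". For parameters recorded more than once in Part A, SAP 7 describes the table layout: "The Level 3 displays will report the paired results for the change from the baseline through Month 4".

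SAP 11 sets out a model for the primary NPRS change. In it, "The baseline pain score will be introduced in the model as a covariate"; Protocol 7.1 says the same. SAP 11 then lists further tables. NeuroQoL, SPP, NCS and QST appear there as summaries by randomised arm and time, with no test, model or contrast attached.

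Four other places bear on these endpoints:

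- **SAP 7.1.** Analyses are to be adjusted for baseline results on which the randomised arms turn out to differ, and the stated purpose is precision. No criterion for differing is given. It continues: "Unadjusted analyses will also be conducted and reported as the first set of analyses presented".
- **SAP 9.2.** The baselines listed there include QST, NCS, SPP and NeuroQoL. They may be added to a model as covariates; nothing requires it.
- **SAP 13.2, item 3.** Generic code for efficacy parameters has terms for treatment, center and baseline. The section opens with the caution "Not all procedures may be required for the presentation of the results from this study", and adds that procedures not directly referenced in the SAP may be used in supportive analyses. No section assigns item 3 to Endpoints 3 to 6.
- **Protocol 7.1.** Pairwise differences between arms are to be given with 95% confidence intervals, with no mention of covariates. Secondary outcomes are to be tested in sequence after the primary. SAP 7.3, by contrast, applies no multiplicity adjustment.

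All four measures are taken at the Enrollment Visit (Protocol 4.3), and SAP 4.1 requires them of all subjects.

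**The concern.** A reader of SAP 11 cannot tell which analysis of Endpoints 3 to 6 is the main one. It could be a raw change compared between arms, or a model containing the measure's own baseline. The choice would turn on an undefined judgement about imbalance, made once the baseline data can be compared by arm.

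The trigger in SAP 7.1 also works against its own purpose. A covariate gains precision through its correlation with the outcome, not through a difference between arms. A baseline that strongly predicts the Month 4 value but happens to be balanced would be left out, although adjusting for it would still help.

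These endpoints carry the quality-of-life and mechanistic conclusions. Whether they are tested in sequence (Protocol 7.1) or each at 5% (SAP 7.3), each needs a test defined in advance. At stake are some power, some protection against chance baseline differences, and a clear choice of headline estimate.

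**Working it through.** **The plan's own figure.** The only sample size is for NPRS: "Based on alpha = 0.05 and 90% power, a sample size of 62 patients per treatment group would be needed". The inputs are an assumed difference ("Assuming a placebo effect of 40% results in an assumed between group difference of 1.07 units"; 1.79 × 0.6 = 1.074), an SD of change of 1.83, and a two-sided 5% level. By the normal formula, n = 2 × (1.960 + 1.282)² × (1.83/1.07)² = 61.5, rounded up to 62 per arm, which reproduces. No SD, effect, power or correlation is stated for Endpoints 3 to 6, so 62 per arm serves below only as a scale.

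**Direction.** Let s0 and s1 be the baseline and Month 4 SDs and r their within-arm correlation.

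- Variance of raw change: s0² + s1² − 2·r·s0·s1.
- Residual variance under ANCOVA: s1²·(1 − r²).
- The first minus the second is (s0 − r·s1)², which is never negative.

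Apart from one degree of freedom for the covariate, ANCOVA is therefore never less precise than raw change, whether or not the arms differ at baseline.

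**Size.** With equal SDs, the two variances are proportional to 2(1 − r) and 1 − r². ANCOVA over raw change is then (1 + r)/2, and the inverse is 2/(1 + r). The values of r below are assumptions. The last column takes an effect that would have 80% power on raw change: power = Φ(2.802/√((1 + r)/2) − 1.960), where 2.802 = 1.960 + 0.842.

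| r | ANCOVA / raw change | Raw change / ANCOVA | Cut in SE with ANCOVA | ANCOVA n per arm matching 62 on raw change | Power, from 80% |
|---|---|---|---|---|---|
| 0.3 | 0.65 | 1.54 | 19.4% | 41 | 93.5% |
| 0.5 | 0.75 | 1.33 | 13.4% | 47 | 89.9% |
| 0.7 | 0.85 | 1.18 | 7.8% | 53 | 86.0% |
| 0.9 | 0.95 | 1.05 | 2.5% | 59 | 82.0% |

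**Chance imbalance.** At 62 per arm, one standard error of the baseline difference is √(2/62) = 0.18 SD. It shifts the raw-change contrast by (1 − r) × 0.18 SD: 0.13, 0.09, 0.05 and 0.02 SD at the four values of r. Suppose, as an assumption, that differing meant a two-sided 5% test. An imbalance of 1 SE (z = 1, below 1.96) would then not trigger adjustment, and randomisation alone would trigger it for only about 1 baseline in 20.

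**The case against.** A reader might infer something stronger: that the plan chooses raw change for these endpoints, gives a baseline covariate to pain alone, and leaves the other collected baselines unused. The documents do not support that.

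- SAP 7.1 speaks of the analyses generally, not only of pain, and its unadjusted results accompany adjusted ones.
- SAP 9.2 allows these four baselines as covariates.
- Item 3 of SAP 13.2 is headed for efficacy parameters in general and contains a baseline term. It is not assigned by name to NPRS either.
- A change score uses the baseline by subtraction.
- Protocol 7.1 does not describe its pairwise differences as unadjusted.
- The Level 3 layout also serves the primary endpoint, which has an adjusted model, so the layout is no evidence that adjustment is absent.
- SAP 15 puts the full table index in a separate file that was not available here.

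It can also be said that the size is hypothetical. The correlation, the equal SDs and the 80% starting power are all assumed. Nor is the change confined to a single column: counted separately, there are 12 NeuroQoL domain scores (six domains, weighted and unweighted), 4 SPP readings, 4 NCS readings and 6 QST thresholds, 26 contrasts in all.

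All of this stands, and it limits the point to underspecification. It does not remove the point: one route to adjustment depends on the observed baselines without a criterion, one is optional, and one is non-binding.

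**Conclusion.** The point holds as a gap in prespecification with a readily available better method. No model containing the measure's own baseline is firmly assigned to Secondary Endpoints 3 to 6, and the SAP 7.1 trigger does not deliver the precision it is meant to deliver.

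If the reported result rests on raw change, its variance is 1.05 to 1.54 times that of ANCOVA for r from 0.9 down to 0.3. Those figures rest on equal SDs at both times and on assumed values of r. If these measures are highly stable over four months, the gain is small. That ANCOVA is no less precise does not depend on equal SDs. The primary NPRS analysis is not affected.

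**What to change.** In SAP 7.1 and SAP 11, replace the imbalance trigger for Secondary Endpoints 3 to 6 with a prespecified ANCOVA, fitted whether or not baselines differ.

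- **Model:** Month 4 value or change (the treatment estimate is the same), with treatment, the measure's own baseline and pooled site. This is item 3 of SAP 13.2; SAP 11 should refer to it by name so that it becomes binding.
- **Site term:** Protocol 7.2 and SAP 7.1 define small sites differently, so state which pooling rule applies.
- **Reporting:** give the adjusted active minus sham difference with its 95% CI as the main comparison. Keep unadjusted changes and the Level 3 tables as descriptive or supportive.

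This does not settle which component represents each endpoint, which the SAP should state separately.

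The cost is one SAP paragraph and added model output for several components per endpoint. It needs no new data and no further patients.
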